6 RISKS AND BENEFITS OF THE DEVICE AND CLINICAL INVESTIGATION

6.1 Anticipated clinical benefits

The BIO|MASTER.Ilivia Family / Plexa study is designed to identify and evaluate residual risks associated with the use of the Ilivia ICD family and the Plexa ICD lead that are unveiled or remained even after risk analysis, risk mitigation and successful conformity assessment. Furthermore, the study aims at providing additional data, as required by regulatory authorities outside the CE-region.

With the participation in this clinical investigation, the patient receives a modern device with many potential clinical benefits. The clinical status of the patient will be intensively supervised during study participation.

All used investigational devices in this clinical investigation will be implanted after CE-certification. In countries located outside the CE area, devices will only be implanted after market or study approval of the responsible regulatory institution. The investigational devices meet the current state of medical science and technology and are used according to their intended use.

The new Plexa ICD lead provides DF-1 and DF4 connector variants with single and dual shock coils and DX variants. Due to the new design of screw and gliding capability of the inner lumen of the lead, an increase of handling comfort of the lead is expected. The twisted cable design is expected to increase durability of the lead.

The new Ilivia family provides new features like MultiPole Pacing (MPP) and DX functionality in CRT-D devices.

MPP enables pacing in two different vectors within the left ventricle if the device is used in combination with a quadripolar left ventricular lead. Studies have shown that pacing via different vectors is beneficial to optimize synchronization of the left ventricle and thus results in an improvement of different parameters of heart failure like ejection fraction, stroke volume, endsystolic volume, and others²⁵⁻²⁸. Furthermore the rate of non-responders to CRT-D therapy is decreased²⁵. Ginks et al. have postulated that patients with myocardial scar or absence of a functional block do benefit from multisite pacing to achieve CRT response³⁰. The optimal site of acute hemodynamic response to CRT varies between patients and thus might require individualization²⁴. Severe scar seems to increase the benefit of multisite pacing compared to conventional biventricular pacing³¹.

The DX functionality, available in all CRT-D devices of the 5 and 7 series Ilivia family, allows right atrial sensing via an atrial bipole on the right ventricular lead if the device is combined with a DX lead. The use of the DX functionality allows reduction of the number of implanted leads in patients who do not require atrial pacing and thus potentially reduces the risks of lead related complications¹⁸⁻²².

In addition to MPP and DX functionality, an additional cycle length for ATP therapy was added to the device programming according to the result of the painFREE trial, which showed that an ATP R-S1 coupling interval of 88% of the cycle length of a fast ventricular tachycardia administered in 8-pulse burst is highly effective to terminate the tachycardia and thus reduces shock administration^{2;3}.

The use of Home Monitoring[®] functionality offers the physicians the possibility to monitor their patients remotely whenever it is deemed necessary. The automatic early detection of arrhythmia and device anomalies allows earlier medical intervention as compared to conventional in-office follow-ups. The results of the TRUST clinical study demonstrated the safety and effectiveness of the remote monitoring³².

The individual benefit of study participation for the patient is an intensified medical supervision of his clinical status. In CRT-D patients the chance of responding to CRT-D therapy might be increased due to MultiPole Pacing.

6.2 Anticipated risks

6.2.1 Anticipated adverse device effects

Adverse device effects anticipated for patients with ICD or CRT-D implantation are described in section 18.7 of the clinical investigation plan.

6.2.2 Residual risks associated with the device

Implantation of the Ilivia ICD family and the Plexa ICD lead does not differ from the procedures applicable for comparable systems. Thus, no additional risks or burdens concerning device implantation derive from participation in the study.

6.2.3 Risk associated with participation in the study

Patients included in the BIO|MASTER.Ilivia Family / Plexa study have an indication for ICD or CRT-D therapy and will be implanted with an implantable cardiac rhythm management device independently from the study. As implantation of the investigational devices used in this study does not differ from standard operation procedure, no study specific risks are associated with the implantation procedure.

Risks associated with MultiPole Pacing

The use of MultiPole Pacing in CRT-D patients requires the implantation of a quadripolar lead (BIOTRONIK Sentus OTW QP). In some cases this lead might not be suitable for implantation due to the individual anatomy of the coronary venous system. The physician will determine if the lead is appropriate for a specific patient during the implantation procedure. In most cases the decision can be made during visualization of the coronary veins, thus the Sentus QP lead will only be implanted in those patients most likely eligible for this LV lead. However, in single cases unsuccessful positioning of a left ventricular lead might occur, requiring lead exchange during implantation. Unsuccessful positioning of a left ventricular lead and exchange of the lead during implantation is common in about 7% to 19% of patients during CRT implantation³³ and can therefore not be accounted for as additional risk of the use of the MultiPole Pacing option. It has even been shown that the use of multipole electrodes increases the implantation success of left ventricular leads since potential problems like phrenic nerve stimulation or high pacing thresholds can be overcome by choosing from the many available pacing vectors.

For the study it is mandatory to measure all available 12 pacing vectors of the LV lead prior to programming of MPP. This measurement will prolong the pre-hospital discharge follow-up of the patient by about 10 minutes.

In about 40% of cases phrenic nerve stimulation occurs in one or more vectors of quadripolar leads, potentially resulting in temporary hiccups or muscle contractions^{34;35}, which disappear

as soon as the threshold is switched off. However, due to the high number of available vector options for MultiPole Pacing, it should be possible to avoid occurrence of phrenic nerve stimulation in the final programmed vectors in nearly all cases.

In total, the use of a second left ventricular pacing stimulus results in a calculated longevity reduction of the CRT-D battery of approximately 10% (6.9 years vs. 6.2 years; assumption: 60ppm, 100% pacing with [contact] in all chambers). For the mandatory activation of the MPP feature during the 6 months duration of the study, this results in a reduction of longevity of about 2.4 weeks, which is clinically not significant and considered acceptable.

The use of the MPP functionality shows no additional risks compared to any standard use of quadripolar left ventricular leads. The expected battery reduction is limited due to the short duration of the study.

Risks associated with DX functionality in CRT-D devices

The use of DX functionality is indicated for patients who do not require atrial pacing, for example patients in atrial fibrillation or patients with normal sinus node function. However, in a proportion of patients an atrial lead might have to be added due to a change of the electrical pattern in the atrium.

In AF patients, the risk of symptomatic bradycardia may be increased after conversion to sinus rhythm due to CRT therapy³⁶ and stimulation of the atrium may be required in case of slow, insufficient sinus rhythm after conversion. However, often it is standard clinical practice that no atrial lead is implanted in patients with permanent atrial fibrillation^{37;38}. Therefore the risk for additional atrial lead implantation would be equal in patients implanted with a DX system and in patients not planned to be implanted with an atrial lead. In hospitals with a standard implantation of the atrial lead in AF patients, the implantation risk will be increased by the use of CRT-DX due to a potential later implantation of an atrial lead. However, the standard implantation of an atrial lead in patients who will not experience conversion to sinus rhythm due to CRT therapy is an unnecessary increase in lead burden¹⁷.

Furthermore, the atrial sensing of the CRT-D device connected to a DX lead might be inferior to a standard atrial lead, despite mostly positive clinical experiences³⁹⁻⁴¹. However this is predominantly a factor for patients in sinus rhythm. In patients with AF the atrial sensing is only diagnostic and not used for the timing of ventricular pacing and not needed for discrimination of different supraventricular tachycardias.

As the use of the DX functionality is not predefined by the BIO|MASTER.Ilivia Family / Plexa study but only based on a physicians` decision in regard to the respective patient, this cannot be counted as a general risk of the study participation.

Further Risks

In the course of the study, event-triggered IEGMs will be transmitted via Home Monitoring[®]. The transfer of these data will result in a reduction of battery lifetime. However, the transmission of event-triggered IEGMs provides physicians with more information on patient status and might therefore be beneficial for the treatment of the patient. The benefit of Home Monitoring has been shown in different trials^{6;32;42} and has led to a wide acceptance of remote patient monitoring in clinical routine. Thus, physicians might choose these options for their patients even if not participating in the study.

All conducted examinations are part of clinical routine. Depending on the specific hospitals` routine, the timing of the in-office follow-ups might deviate slightly from the routine. However, otherwise no additional burden for the patient due to the study participation is expected.

6.2.4 Possible interactions with concomitant medical treatments

For ICD and CRT therapy, no interactions with concomitant medication or medical treatment are expected.

6.3 Steps to control or mitigate the risks

The risks can be minimized through the utilization of strict aseptic technique, compliance with the technical manual, compliance with this clinical investigation plan and technical procedures, adhering to the guidelines for selection of patients, close monitoring of the patient's physiologic status during the procedures, and by promptly supplying BIOTRONIK with all pertinent information required by this clinical investigation plan.

6.4 Risk-to-benefit rationale

Patients are provided with the newest available BIOTRONIK CRT-D or ICD technology. Only CE approved devices and leads will be used in this clinical investigation. The implantation procedure does not differ from other comparable CRT-D/ICD system implantations, thus resulting in no additional risk for the patient.

The Plexa ICD lead is the successor of the well-proven Linx^{smart} / Protego DF-1 (DX) and DF4 leads. The Ilivia/Intica/Inlexa ICDs are based technically and functionally on the CE-approved Inventra/Iperia/Itrevia family. Furthermore most of the new features are based on already market approved and proved BIOTRONIK pacemaker and ICDs.

The devices combine the classical benefit of ICD therapy with bradycardia and CRT therapy. All functional extensions of the ICD family are functions that have proven to be beneficial in clinical usage and their therapeutic benefit has been demonstrated.

The use of MPP in CRT-D patients carries the same risks as the use of any quadripolar lead. Furthermore the battery depletion of the feature with 2.4 weeks reduction of longevity for the duration of the study is negligible. However, multisite pacing has been shown already beneficial to increase the responder rate to CRT-D therapy. Possible occurrence of phrenic nerve stimulation can easily be avoided due to the high number of available vector combinations.

The use of DX functionality in CRT-D patients carries the risk of possible re-implantation of an additional atrial lead, if required. However, implantation of an atrial lead in the beginning, if not needed, might increase the lead burden. As the use of DX functionality is not mandatory in the present study, the decision to use the DX functionality is based on the physicians' discretion and thus cannot be accounted for as additional risk of the study.

The mandatory use of Home Monitoring and transmission of IEGMs decreases battery lifetime. However, the transmission of recording episodes IEGMs provides physicians with more information on patient status and might therefore be beneficial for the treatment of the patient. Thus, physician might choose these options for their patients even if not participating in the study.

In summary, the potential benefits of the study participation for the patient exceed the potential risks. Taking risks and benefits into account it can be stated that study participation of the individual patient can be regarded as justifiable.

7 OBJECTIVES

7.1 Objectives

This study is designed as post market clinical follow-up study to identify and evaluate residual risks associated with the use of the Ilivia ICD family and the Plexa ICD lead that are unveiled or remained even after risk analysis, risk mitigation and successful conformity assessment. Furthermore, the study aims at providing additional data, as required by regulatory authorities outside the CE-region. The results will be used for updating the clinical evaluation.

7.1.1 Primary Objectives

7.1.1.1 **Group A:** Ilivia family related safety through 3 months

This objective of the clinical investigation is to confirm the clinical safety of the Ilivia ICD family by the analysis of the Ilivia related SADEs within 3 months after implantation.

7.1.1.2 **Group B:** Plexa related safety through 3 months

This objective of the clinical investigation is to confirm the clinical safety of the Plexa ICD lead by the analysis of the Plexa related SADEs within 3 months after implantation.

The safety objectives for both groups are defined for a 3-month follow-up period, as the majority of, for example, lead complications is found within this early postoperative phase ^{43;44}.

7.1.2 Secondary Objectives

7.1.2.1 Secondary objectives **Group A:** Ilivia family

7.1.2.1.1 Conversion of fast ventricular arrhythmia (detection in VF zone) by ATP one shot through 6 months

This efficacy objective is to confirm the effectiveness of ATP one-shot at the newly recommended programming (8 pulses with 88% R-S1) in the Ilivia ICD family within 6 months after implantation. This objective will be assessed through 6 months after implant to increase the chance of appropriate ICD therapy experienced by patients, as the number to be expected is relatively low. Moss et al. reported an incidence of about 10% within 6 months after implantation ⁴⁵.

7.1.2.2 Secondary objectives **Group B:** Plexa

7.1.2.2.1 Right ventricular sensing at 3-month follow-up

This efficacy objective of the clinical investigation is to confirm the appropriate sensing in the Plexa ICD lead within 3 months after implantation. This objective will be assessed at the 3-month follow-up, as lead ingrowth is expected to be completed until that time and thus measured values display the normal function in the patient. The purpose of the secondary endpoint is to evaluate the ability of the Plexa ICD lead to appropriately sense the intrinsic cardiac signal.

7.1.2.2.2 Right ventricular pacing at 3-month follow-up

This efficacy objective of the clinical investigation is to confirm the appropriate pacing in the Plexa ICD lead within 3 months after implantation. This objective will be assessed at the 3-month follow-up, as lead ingrowth is expected to be completed until that time and thus

measured values display the normal function in the patient. The purpose of this secondary endpoint is to evaluate the ability of the Plexa ICD lead to appropriately stimulate the cardiac tissue.

7.1.3 Further efficacy objectives

The further objectives are to describe the performance and efficacy of the new available features in the Ilivia ICD family and the Plexa ICD lead.

7.2 Safety assessments

Risks and anticipated adverse effects as described in section 6.2 will be assessed.

8 DESIGN OF THE CLINICAL INVESTIGATION

8.1 General considerations

The study is designed as a multicenter, international, non-randomized, open-label and prospective study including two subgroups: **group A** with the Ilivia ICD family and **group B** with the Plexa right ventricular ICD lead.

Patients can be enrolled into both groups, if they receive both study devices, see below for details.

Group A
Ilivia ICD family

Enrollment:

In group A, a total of 105 patients will be enrolled. With an expected drop-out rate of 10% a minimum number of 94 patients will be included in the analysis set. In total, 26 patients should receive a single chamber ICD, 26 patients a dual chamber ICD and 53 patients a triple chamber ICD (CRT-D).

Group B
Plexa ICD lead

Enrollment:

In group B, a total number of 185 patients will be enrolled. With an expected drop-out rate of 10% a minimum number of 166 patients will be included in the analysis set.

Tab. 4: Required visit windows (1 month is defined as 30 days)

	Window	Days post-implant
Pre-hospital discharge or wound check	+ 10 days	0 to 10
3 months post-implant	± 30 days	61 to 121
6 months post-implant	± 30 days	151 to 211

[figure not shown]

Fig. 4: Follow-up scheme of group A (Ilivia ICD family) and group B (Plexa ICD lead)

Patients in group A and/or group B will be followed for duration of 6 months in the BIO|MASTER.Ilivia Family / Plexa study. During this time 5 visits are planned per patient: Enrollment, Implantation, Pre-hospital discharge, 3-month follow-up and 6-month follow-up (Fig. 4). The implantation shall be performed within 30 days after enrollment of the patient. The other windows associated with each visit are provided above in Table 4. This schedule should be followed as closely as possible. If circumstances prevent the presence of the patient at the follow-up visit, the reason for the missed follow-up has to be indicated on the eCRF. In addition, interim evaluations for device related revisions will be performed.

Patients in both groups A and B: It is recommended that patients are implanted with both investigational devices, the Ilivia ICD family **and** Plexa ICD lead, Figure 5. Such patients can belong to both study groups and should then complete all follow-ups as required by both groups. The participation in both groups instead of only in group A or in group B can be freely chosen by the investigator based on his/her medical opinion. However, the investigation should be compliant with the study protocol for group A, group B or both, respectively.

The enrollment of patients in both study groups will be stopped independently. The project management of the BIO|MASTER.Ilivia Family / Plexa study will inform all investigators in advance in written form about the stop of enrollment of patients to both groups A and B.

After 105 patients have been enrolled into group A, or 185 into group B, further patients can receive both Ilivia and Plexa implants, but can only be enrolled into the group which is still open for enrollment. These patients are not subject to CIP required procedures related to endpoints of the group into which they have not been enrolled, and if endpoints are recorded by oversight of the investigator, they will be excluded from the analysis.

Furthermore, in case a patient enrolled in both groups, is exited from one of the groups, only data for the still active group will be provided and used for analysis from that point in time on.

[figure not shown]

Fig. 5: Overlap of both study groups. Patients implanted with an ICD device of the Ilivia family and a Plexa ICD lead can belong to both groups A and B

A study duration of about 14 months enrollment plus 6 months FU = 20 months is expected in total. First Patient In (FPI) is expected for beginning of June 2016. Last Patient In can be expected for end of July 2017 (LPI), which means that the last patient will leave the study end of January 2018 (LPO, Last Patient Out).

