8.3 Endpoints and hypotheses

8.3.1 Primary endpoints and hypotheses

The global primary hypothesis consists of two primary hypotheses related to the SADE-free rate in group A and SADE-free rate related in group B, respectively. The global primary alternative hypothesis is accepted when the primary alternative hypothesis for group A or the primary alternative hypothesis related to group B, or both can be accepted.

8.3.1.1 **Group A:** Ilivia family related SADE-free rate through 3 months

The safety of the Ilivia ICD family will be evaluated by asking the investigator to record any adverse event. While all adverse events have to be recorded throughout the study, only the Serious Adverse Device Effects (SADE) possibly or securely related to the Ilivia ICD family devices (SADE-d_{Ilivia}) until 3-month follow-up are counted for this primary endpoint. Securely procedure related Serious Adverse Device Effects (SADE-p_{Ilivia}) are not counted. Further definitions are given in section 18.11. The primary hypothesis evaluates the SADE-d_{Ilivia} free rate (Ilivia_{SADE_free}). It is expected, that the rate will be significantly above 90%, the corresponding hypotheses definitions are:

Null hypothesis: $H_{0_Ilivia} : Ilivia_{SADE_free} \leq 90\%$

Alternative hypothesis: $H_{A_Ilivia} : Ilivia_{SADE_free} > 90\%$

The parameter of interest "Ilivia_{SADE_free}" is the device related SADE-d free rate per patient, which will be calculated by

$$Ilivia_{SADE_free} = [1 - \text{number of patients with one or more ICD related SADEs (SADE-d}_{Ilivia}\text{) until 3-month follow-up divided by all patients in the analysis set}] * 100\%.$$

SADEs will be adjudicated by an internal adjudication board, whereby the seriousness and device relatedness will be re-examined. If any amply documented external physical influence (e.g. accident, sport, twiddling) or medical AE caused the SADE, it does not contribute to this endpoint. SADEs that occur later than the 3-months follow-up do not contribute to this endpoint.

8.3.1.2 **Group B:** Plexa related SADE-free rate through 3 months

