9 STUDY PROCEDURES

9.1 Overview

Table 7 provides an overview of the study procedures.

Tab. 7: Time schedule and procedures for all patients. Group specific procedures of group A are displayed in blue, and group specific procedures of group B are displayed in green.

Investigations	Enroll-ment	Implan-tation	Pre-hospital discharge	Month 3 ± 30 days	Month 6 ± 30 days
Patient informed consent	x				
Verification of in- and exclusion criteria	x				
Demographic data	x				
Indication for ICD or CRT-D therapy	x				
ECG diagnostics (if available)	x				
NYHA class (if available)	x				X (CRT-D only)
Heart Failure Parameters (LVEF) (if available)	x				
Physicians evaluation responders/non-responders (CRT-D only)					x
Co-morbidities	x				
Cardiovascular medication	x				
Decision on group participation		x			
ICD/CRT-D system implantation		x			
Information / Measurements on DX devices (only if DX is implanted)		x	x	x	x
Device statistics CRT pacing, atrial burden (CRT-D only)			x	x	x
Programming/Handling/Change of programming of MPP		(x)	x	x	x
Programming of device settings		(x)	x		
Programming / Information on Early ATP one-shot		x			
Lead measurements with PSA		x			

Document the handling of Plexa ICD lead		x			
IEGMs of pacing and sensing test / Evaluation of appropriate sensing/pacing				x	
IEGMs / evaluation of ATP one shot success		x	x	x	x
IEGMs and documentation of ventricular tachycardia therapy episodes		x	x	x	x
IEGMs and documentation of the last 3 episodes with fast ventricular rhythm (e.g. SVTs, nVTs) prior to a follow-up		x	x	x	x
Lead measurements		x	x	x	x
IEGMs of all medical episodes (ventricular and atrial episodes, non-sustained VTs and fast intervals)		x	x	x	x
Documentation of MRI examinations, if applicable		x	x	x	x
Adverse event reporting	x	x	x	x	x
Device deficiency reporting		x	x	x	x
Regular study termination					x

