9.3 Implantation

All patients will be **either** implanted with one of the Ilivia ICDs (**group A**) **and/or** the Plexa ICD lead (**group B**). If both devices are implanted patients will participate in both groups as long as enrollment in both groups is still ongoing. Implantation shall be performed within 30 days after enrollment of the patient to the study.

Patients with planned pacemaker or ICD upgrade to ICD or CRT-D or exchange can also be included in the study (**group A** only).

The specific requirements of the implantation procedures are listed below:

1. Perform lead measurements prior to connection to the device. For patients in **group B** only measurements of the RV lead are required. Pacing thresholds for RA and RV lead have to be measured at a pulse width of 0.4ms. For CRT patients in **group A**, threshold measurements of at least the 6 recommended LV vectors is recommended to ensure availability of a suitable vector combination for MPP programming.
2. After lead connection to the ICD or CRT-D device, the following data have to be recorded during this follow-up:
 - Pacing thresholds measured manually or triggered automatically. In the RA and RV the pulse width must be 0.4 ms, in the LV any pulse width can be chosen. For patients in **group B** only measurement of the RV lead is required. For CRT-D patients in **group A** pacing thresholds in all 12 available LV vectors have to be measured, if MPP programming is already planned at this point in time.
 - P/R-wave sensing amplitude (mean value) of all channels (or RV lead only (**group B**)) including also atrial sensing amplitude in DX leads.
 - Pacing impedance of all channels (or RV lead only (**group B**)). For the LV channel, measurement of the pacing threshold automatically also provides impedance measurement values.
 - Painless shock impedance Pacing polarities of the LV channels (CRT-D only (**group A**))
3. **Group A:** Program and document settings for MPP and evaluate handling of the programming function of the programmer. For programming follow the recommendations provided in section 8.5.6. Document all information on the eCRF "MultiPole Pacing". MPP programming can be delayed but has to be finalized latest at Pre-hospital discharge.

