11.3 Level of significance and the power of the study

The 2-sided level of significance is $\alpha = 2.5\%$ for each alternative hypothesis (1-sided 1.25% significance level). Thus, the 2-sided significance level of the global hypothesis of 5% (1-sided 2.5% significance level) is maintained.

A minimum statistical power for primary hypothesis 1 of 80% and a minimum power of 90% for primary hypothesis 2 were used for sample size calculation.

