7.3. Plexa Analysis Set

Similar to the definition of the Ilivia analysis set (see chapter 7.2), the Plexa analysis set consists of all patients in group B and in group AB, who met all in- and exclusion criteria. Patients who did not come in contact with any Plexa lead are not included in the analysis set.

Data file, identifier patient_display_id_full	Variable name	Variable label	Variable level	Nominal values
enrollment	DMSUBIC	Patient has provided written informed consent	nominal	Yes /No
enrollment	TIINCL01 TIINCL02 TIINCL03 TIINCL04 TIINCL05 TIINCL06	Inclusion criteria [...]	nominal	Yes /No
enrollment	TIEXCL01 TIEXCL02 TIEXCL03 TIEXCL04 TIEXCL05 TIEXCL06 TIEXCL07	Exclusion criteria [...]	nominal	Yes /No
implantation_gene ral_data	imp_group	Patient Group		Device of the Ilivia family (group A) Plexa right ventricular lead (group B) Both Ilivia and Plexa (group AB)
study_termination	end_early_b	Reason for early study termination	nominal	Implantation of Plexa lead was planned but not performed (patient did not come in contact with the investigational device) [...]
study_termination	end_early_ab	Reason for early study termination	nominal	Implantation of Ilivia ICD family and Plexa lead were planned but not performed (patient did not come in contact with the investigational devices) [...]
data_SAR	analysis_set_Plexa_ SAR ⁶	Analysis set Plexa	nominal	Yes / No

⁶ IF DMSUBIC = Yes AND
 TIINCL01 = Yes AND TIINCL02 = Yes AND TIINCL03 = Yes AND
 TIINCL04 = Yes AND TIINCL05 = Yes AND TIINCL06 = Yes AND
 TIEXCL01 = No AND TIEXCL02 = No AND TIEXCL03 = No AND
 TIEXCL04 = No AND TIEXCL05 = No AND TIEXCL06 = No AND TIEXCL07 = No AND
 (imp_group = ... (group B) OR imp_group = ... (group AB)) AND
 end_early_b ≠ Implantation of Plexa lead was planned but not performed ... AND
 end_early_ab ≠ Implantation of Ilivia ICD family and Plexa lead were planned but not performed ...
 THEN analysis_set_Plexa_SAR = Yes
 ELSE analysis_set_Plexa_SAR = No

8. General data

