16.6. Hypotheses & Statistical Tests

CIP chapter 8.3.1.1 Group A: Ilivia family related SADE-free rate through 3 months

Null hypothesis: $H_{0_Ilivia} : Ilivia_{SADE_free} \leq 90\%$

Alternative hypothesis: $H_{A_Ilivia} : Ilivia_{SADE_free} > 90\%$

CIP chapter 11.1. Statistical design, methods and analytical procedures

For both primary hypotheses exact binomial tests are carried out.

CIP chapter 11.2. Sample size

A correction for multiple testing is considered by adjusting the significance level.

CIP chapter 11.3. Level of significance and the power of the study

The 2-sided level of significance is $\alpha = 2.5\%$ for each alternative hypothesis (1-sided 1.25% significance level)

A one-sided exact binomial test is carried out for the significance level 1.25%. Additionally, a two-sided 97.5% confidence interval for an exact binomial test is calculated.

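### Two rules conflict on whether a patient with both devices joins one group or both, and the choice is made at the implantation visit, so an endpoint event already known then can be kept out of that device's primary rate, mainly in group B

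*Protocol*

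**What the plan says.** Two current protocol rules govern a patient who receives both an Ilivia ICD and a Plexa lead.

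- Protocol 8.1: "participation in both groups instead of only in group A or in group B can be freely chosen by the investigator". The sentence goes on to base the choice on the investigator's medical opinion, and the next one asks for compliance with the protocol for whichever group or groups apply.
- Protocol 9.3: "If both devices are implanted patients will participate in both groups as long as enrollment in both groups is still ongoing".

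On timing, the row "Decision on group participation" in Table 7 (Protocol 9.1) is marked only under Implantation. Protocol 9.2 lists what the Enrollment and Baseline eCRFs record, and neither list contains a planned device or group.

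On analysis, SAP 7.3 states that "the Plexa analysis set consists of all patients in group B and in group AB, who met all in- and exclusion criteria". SAP 7.2 does the same for groups A and AB. Footnotes 5 and 6 take the group from imp_group on the implantation form. The primary endpoint flags (footnotes 72, 73, 99 and 100) then require membership of that set.

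**The concern.** The study is single-arm and open-label, and each primary endpoint is tested against a fixed 90%. With no control arm to share a selection effect, anything that removes event patients from a group raises its SADE-free rate directly, and an exact test gives no protection.

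Under the 8.1 rule, an investigator who has implanted both devices and already knows of a Plexa event when the implantation form is completed may enter the patient in group A only. That patient is then in neither the numerator nor the denominator of the Plexa rate. Under the 9.3 rule this could not happen while both groups are open. The plan does not say which rule prevails, and it asks for no pre-implant record against which the choice could be checked.

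**Working it through.** **Inputs**

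- Null SADE-free rate 90% in both groups. Protocol 8.3.1: "It is expected, that the rate will be significantly above 90"%.
- Level, Protocol 11.3: 2.5% two-sided "for each alternative hypothesis (1-sided 1.25% significance level"). SAP 16.6: "A one-sided exact binomial test is carried out for the significance level 1.25"%; SAP 23.6 is the same for Plexa.
- Power, Protocol 11.3: "minimum statistical power for primary hypothesis 1 of 80% and a minimum power of 90% for primary hypothesis 2".
- Assumed SADE-free rates 98% (A) and 97% (B), with 94 and 166 evaluable patients and 105 and 185 enrolled (Protocol 11.2).

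**Step 1. Reproduce the plan's figures.** With X the number of event patients, the test passes at X ≤ c, where c is the largest value with P(X ≤ c | n, 0.10) ≤ 0.0125.

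| Group | n | c | P at c | P at c + 1 | Power at the assumed rate |
|---|---|---|---|---|---|
| A | 94 | 3 | 0.01246 | 0.0357 | 88.0% |
| B | 166 | 8 | 0.01215 | 0.0260 | 93.6% |

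One patient fewer misses the power target in each group: n = 93 gives c = 2 and 71.5%; n = 165 gives c = 7 and 87.5%. Enrolled numbers are 94/0.9 → 105 and 166/0.9 → 185. At n = 185, c = 9. All of this agrees with Protocol 11.2 and with the termination limits in 11.7 (4 in A; 9, or 10 with few drop-outs, in B). The sample size is sound.

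**Step 2. What one patient decides.** In group B, 9 events in 166 fail (p = 0.026) and 8 in 166 pass (p = 0.012). Moving one event patient to group A only and filling the place with an event-free patient turns a fail into a pass. Without replacement it would not: 8 in 165 gives p = 0.0129, just above 0.0125. Enrollment into B runs to a fixed target of 185 members, so replacement is the natural case.

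**Step 3. Illustration over an assumed share.** Let d be the share of event patients not entered in the group. The documents give no value for d. At a true event rate of 10%, the event rate among those entered is

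q = 0.10(1 − d) / (1 − 0.10d).

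For group B, n = 166, c = 8:

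| d | q | P(X ≤ 8) |
|---|---|---|
| 0 | 0.1000 | 1.2% |
| 5% | 0.095/0.995 = 0.0955 | 1.9% |
| 10% | 0.090/0.990 = 0.0909 | 3.0% |

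**Step 4. Who can be affected.** An affected case needs all of the following:

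1. The patient receives both devices.
2. The event meets the endpoint definition in Protocol 18.11.
3. The event is known when the group is recorded.
4. Both groups are open. Protocol 8.1 closes group A at 105, after which a Plexa recipient has no group A to be entered in.

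The events foreseeable at implant are mostly lead events, which is why the exposure lies mainly in group B.

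**The case against.** The strongest reply is that the plan already implies an intended group before implant.

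- Protocol 8.8.1 enrolls patients planned for Ilivia, Plexa or both. Some eligibility criteria depend on the group (upgrade or exchange in 8.8.2, willingness to activate MultiPole Pacing in 8.8.3) and are checked at enrollment.
- The reference to medical opinion in 8.1 can be read as governing the choice of devices, with 9.3 then assigning the group.

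This stands as evidence of intent. It does not settle the conflict, because the text of 8.1 speaks of group participation and no form is said to hold the intended group.

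A reader might infer that a failed Plexa attempt, with another lead left in place, may simply be coded as group A. The documents do not support that. Protocol 8.8.4.1 and 9.8 make such a patient a group B drop-out, 8.6 bars replacement after device contact, and the SAP removes only patients without contact. Coding the patient as group A would be a deviation. What remains is that nothing recorded before implant would reveal it.

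A reader might also infer that implant complications in general can be hidden. That goes too far. Difficult fixation is not in itself a SADE, securely procedure-related SADEs are not counted (8.3.1, 18.11), and a dislodgement found after the visit comes too late if the form is completed immediately, as 9.3 asks. The protocol's own timing evidence is the early postoperative phase (7.1.1) and, for the predecessor lead, dislodgements within 3 months (5.2.5). Neither shows that events are known when the group is chosen.

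Finally, exposed patients stay traceable. All adverse events are assessed against the investigational devices (8.5.15), serial numbers are recorded (4.4, 15), and SAP 10.2 tabulates Plexa versus other RV leads in the Ilivia set. This allows a listing; it does not correct the primary rate.

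**Conclusion.** The point holds in a limited form. Protocol 8.1 and 9.3 contradict each other, the group is decided at the implantation visit with no specified earlier record, and both primary analysis sets rest on that decision. A stated rule therefore permits selection after exposure in a single-arm test that one patient can decide (8 against 9 of 166).

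The size is uncertain and probably modest. The rise from 1.2% to 1.9% or 3.0% rests on an assumed loss of 5% or 10% of all event patients through 3 months, a true rate exactly at 90%, and replacement up to the planned n. The conditions on who can be affected make large shares hard to justify. For group A the documents suggest no comparable mechanism, and the earlier ICD-related SADE counts they cite are low (2 of 183, none in the DF4 study, 1 of 143).

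It would be wrong to conclude that diversion took place or that the primary results are biased; the documents show only that the rules leave room for it. This should be changed because the correction is cheap.

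**What to change.** 1. In Protocol 8.1, delete the sentence giving the investigator free choice of group and keep the 9.3 rule: both devices means both groups while both are open.
2. In Table 7, move the group decision from Implantation to Enrollment, and record the planned device(s) and group(s) on the Enrollment eCRF before the implant attempt.
3. In SAP 7.2 and 7.3, define each primary set by planned group with device contact, so that attempted implants stay in.
4. For patients already entered, add a sensitivity SADE-free rate for each device over all consented, otherwise eligible patients who received it or were attempted with it while its group was open. List exposed patients outside the group, with their SADEs.

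The cost is one deleted sentence, one moved table row, one eCRF field, revised SAP wording, one sensitivity analysis and one listing. The planned numbers of 94/105 and 166/185 stand. The drawback is that sites lose the option of entering a both-device patient in one group only, and the reported rate may be slightly less favourable.
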